3.1.3 EXPLORATORY OBJECTIVES

- 1. To assess the effect of CD24Fc on aortic vascular inflammation as measured by standardized uptake value of arterial FDG by PET/CT. We will select 12 subjects with an LDL>125 to have the imaging study.
- 2. To assess the effect of CD24Fc on the inflammatory markers hs-CRP and GlycA.
- 3. To assess the effect of CD24Fc on the CEC and NMR lipoproteins.
- 4. To assess the effect of CD24Fc on endothelin-1.

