3.1.5 SECONDARY ENPOINTS

- 1. Percent change in levels of total cholesterol, HDL, and triglycerides from baseline to Week 6 and 28 between placebo and intervention arms.
- 2. Percent change in markers of immune activation (CD4 and CD8 T cells, IFN, TNF, sCD14) from baseline to Week 6 and 28 between placebo and intervention arms.
- 3. Change in proviral DNA from baseline to Week 6 and Week 28 between placebo and intervention arms.
- 4. Percent change from baseline to week 28 in Troponin I and T between placebo and intervention arms.
- 5. Change in percent of hepatic steatosis (by CAP measurement) and fibrosis (by KPA) as determined by transient elastography from baseline to week 28 between placebo and intervention arms.
- 6. Percent change in leptin from baseline to Week 6 and Week 28 between placebo and intervention arms.
- 7. Percent change in hemoglobin A1c from baseline to Week 6 and week 28 between placebo and intervention arms.
- 8. PK and PD assessments (For 6 subjects)
- 9. Presence of ADA and its effect on PK in all subjects

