3.1.6 EXPLORATORY ENDPOINT

- Change in vascular inflammation as evidenced by aortic FDG uptake by FDG-PET/CT will be assessed before and after therapy. The arterial uptake of FDG is measured by the standardized uptake value (SUV) max divided by the venous SUV mean yielding a target to background ratio (TBR).
- 2. Changes in hs-CRP and GlycA before and after treatment.

- 3. Changes in CEC and NMR lipoproteins before and after treatment.
- 4. Changes in endothelin-1 before and after treatment.

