- Vascular inflammation, as measured by FDG-PET/CT
 A major challenge in pilot studies attending to study impact of interventions on CVD risk is the requirement of large sample sizes. Recent studies demonstrated that arterial inflammation may be a valuable surrogate marker for CDV risk ³³⁻³⁶. ¹⁸F-fluorodeoxyglucose (FDG) uptake is a sensitive and reliable marker of atherosclerotic inflammation, and this test will be done at the NIH. Measurements will be performed with the ascending aortic root 18F-FDG standardized uptake values (SUVs) as the maximal SUVs using regions of interest. At the same time, blood-pool SUV in the same superior vena cava will also be measured. The maximal SUV will be divided by the blood-pool SUV, yielding a target-to-background ratio (TBR). The average value will be calculated, and the degree of inflammation will be defined based on the TBR value. For our studies, TBR for 12 HIV subjects with LDL levels greater than 125 mg/dL will be imaged before day 0. These subjects will have a repeat FDG PET/CT at week 24 This allows us to compare the mean TBR score using unpaired t tests.

Results of subject's laboratory values and radiologic assessments will be discussed at the completion of study or during the study, in the event of laboratory or imaging abnormalities which require follow-up.

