9.4.2 ANALYSIS OF THE PRIMARY EFFICACY AND SECONDARY ENDPOINTS

The primary efficacy and secondary analysis will be based on the mITT set. Most of primary and secondary variables such as T cell surface markers and plasma cytokine levels, and change and percent change from baseline to week 28 on markers of vascular inflammation and myocardial damages will be viewed as continuous variables and transformed as necessary. Each of efficacy variables will be analyzed using an Analysis of Covariance (ANCOVA) model with treatment as the fixed effect and other potential risk factors such as baseline value, clinical measures and demographic information as covariates. Differences between treatment groups and 95% confidence intervals will be estimated within the framework of ANCOVA. The statistical test for each of those variables will be a two-sided test at a significance level of 0.05 and no multiplicity adjustment will be done.

Specific details will be provided in the full statistical analysis plan (SAP) for the study.

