Summary statistics for laboratory values will be provided at baseline, post baseline, and for changes from baseline to post baseline. Vital signs will also be summarized in the same way. Occurrence of significant laboratory abnormalities will be tabulated. All medications administered during the study period must be documented on the Concomitant Medication electronic case report form (eCRF). These medications will be coded using the most current version of the World Health Organization Drug Dictionary. A listing of all medications including the reported term, dictionary term, start and stop dates, and other relevant data will be provided. The Safety Analysis Set (SAF) will include all subjects who received at least 1 dose of study medication and the subjects will be analyzed as treated. The safety and efficacy analyses will be summarized based on the SAF.

The following analysis sets will be used in this trial:

- Intention-to-Treat (ITT) Analysis Dataset this includes all randomized subjects
- Modified Intention-to-Treat Analysis Dataset (mITT) this includes all randomized subjects with at least one application of study drug
- Safety Analysis Dataset- this includes all randomized subjects with at least one application of study drug
- Per-Protocol Analysis Dataset this includes a subset of the subjects in the ITT analysis set who complied with the protocol sufficiently to ensure that these data would be likely to represent the effects of study intervention according to the underlying scientific model (e.g., subjects who took at least 80% of study intervention treatment for at least 80% of the initial 4 weeks).

A blinded data review will be conducted prior to unblinding of subject's treatment assignment. This review will assess the accuracy and completeness of the study database, subject evaluability, and appropriateness of the planned statistical methods. For descriptive statistics categorical data will be presented as frequencies and percentages. Percentages will be based on the number of subjects with non-missing values for the corresponding categorical variable. Continuous data will be presented as number of subjects with non-missing values, mean standard deviation, median, minimum and maximum, as well as the 25th and 75th percentile.

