All statistical tests as well as the confidence intervals will be two-sided. The type I error probability for the confirmatory analysis is set to 5%. 95% confidence intervals are to be calculated, if feasible. Covariates for the primary analyses will be pre-specified. For secondary analyses these will be specified later in the SAP.

The primary efficacy and secondary analysis will be based on the mITT set. Most of primary and secondary variables such as T cell surface markers and plasma cytokine levels, and change and percent change from baseline to week 36 on markers of vascular inflammation and myocardial damages will be viewed as continuous variables and transformed as necessary. Each of efficacy variables will be analyzed using an Analysis of Covariance (ANCOVA) model with treatment as the fixed effect and other potential risk factors such as baseline value, clinical measures and demographic information as covariates. Differences between treatment groups and 95% confidence intervals will be estimated within the framework of ANCOVA. The statistical test for each of those variables will be a two-sided test at a significance level of 0.05 and no multiplicity adjustment will be done.

Timing of DSMB Meetings

Timeline	Type of Data
Prior to study dosing	Review charter, Review protocol, Select
, .	roles of DSMB members
Every Six Months	Enrollment summary, adverse events
	listings and tables for primary
	endpoints available.
Medical Monitor report	Review for determination of need for
every 12 weeks	additional DSMB review prior to next
	meeting
If two subjects have same	AE reviews, response to continue or
G4 event related to study	revert enrollment and dosing hold
drug	
If one or more subjects	Review of events with determination of
have mental status	study termination or continuance
changes, DIC, dyspnea,	
cytokine release syndrome	
or hypotension not	
remediated within 2-4	
hours and categorized as	
clinically relevant by PI and	
Medical Monitor with risk	
to participants	
Unanticipated Problem or	Review for determination of need for
non-SAE	additional DSMB review prior to next
	meeting
Upon completion or	Enrollment summary, adverse events
termination of study	listings and tables for primary
	endpoints available.

Study Termination

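### Section 8.2 plans unpaired t-tests of mean TBR in 12 people scanned twice without naming the groups compared; separately, Appendix A's analysis text cites a Week 36 that no visit reaches.

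*Combined protocol and SAP*

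**What the plan says.** The exploratory objective in Section 3.1.3 is "To assess the effect of CD24Fc on aortic vascular inflammation as measured by standardized uptake value of arterial FDG by PET/CT", in 12 participants with LDL above 125. Section 3.1.6 words the endpoint as "Change in vascular inflammation as evidenced by aortic FDG uptake by FDG-PET/CT will be assessed before and after therapy" and names no arms. Section 8.2 describes a scan before Day 0 and a repeat scan, then gives the only test named for TBR: "These subjects will have a repeat FDG PET/CT at week 24 This allows us to compare the mean TBR score using unpaired t tests".

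Section 9.4.2 is headed primary efficacy and secondary endpoints, but its list of variables includes "change and percent change from baseline to week 28 on markers of vascular inflammation and myocardial damages". It analyses each efficacy variable by ANCOVA with treatment as the fixed effect and "other potential risk factors such as baseline value, clinical measures and demographic information as covariates". Details are left to a SAP to be finalised before unblinding.

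Appendix A, under Safety and Efficacy Analyses, repeats the Section 9.4.2 paragraph almost word for word, but with a different week: "change and percent change from baseline to week 36 on markers of vascular inflammation and myocardial damages". Section 3.1.5 sets the related secondary endpoint as "Percent change from baseline to week 28 in Troponin I and T between placebo and intervention arms", and Appendix A's own endpoint list says the same.

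**The concern.** The t-test sentence follows directly from the description of two scans in the same people. The most natural reading is therefore that mean TBR before treatment is compared with mean TBR after it. That has two faults. The two sets of scans are not independent, so an unpaired test uses the wrong standard error. And a before/after comparison, whether pooled over arms or made within one arm, does not estimate the effect of CD24Fc against placebo, which is what the objective asks for.

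The other reading compares the arms. An unpaired test is then a proper form, but Section 8.2 does not say whether follow-up TBR or change in TBR is compared, and neither is the ANCOVA of Section 9.4.2. With 12 people and several possible analyses, the choice should be fixed before unblinding.

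The Week 36 wording is a separate matter: as written, it asks for an analysis of data that will not exist.

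**Working it through.** **Inputs from the documents.** 12 people are scanned before Day 0 and again (Section 8.2). Randomisation is 1:1 (Section 6.3). The Week 28 visit window is ±1 week, and ±30 days for PET/CT (Section 1.3). The documents give no sample-size figure for TBR. Their only one, for LDL, reproduces: 2 × (1.960 + 0.842)² × 20² / 15² = 27.9, so 28 per arm. Nothing below depends on it.

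**Assumptions.** The documents give no TBR standard deviation, effect or within-person correlation r. I take equal SD at both scans, r from 0.3 to 0.9, an effect of 0.6 SD, a 6:6 split and 12 completers. Tests are two-sided at 5%, by simulation (1,000,000 runs for pooled size, at least 400,000 for power).

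**Before/after reading.** With n people, the variance of the mean difference is 2σ²(1 − r)/n. The unpaired test uses 2σ²/n, so its standard error is too large by 1/√(1 − r). True size against a nominal 5%:

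| r | SE too large by | Pooled, n = 12 | Within one arm, n = 6 |
|---|---|---|---|
| 0.3 | 1.20 | 2.2% | 2.5% |
| 0.5 | 1.41 | 0.9% | 1.2% |
| 0.7 | 1.83 | 0.17% | 0.41% |
| 0.8 | 2.24 | 0.03% | 0.17% |

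A paired test holds 5% throughout. Within the active arm (n = 6, 0.6 SD), power at r = 0.5/0.7/0.8 is 10/8/7% unpaired and 22/34/47% paired.

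**Between-arm reading.** With m per arm, the variance of the treatment difference is 2σ²/m for follow-up only, 2σ²·2(1 − r)/m for change, and about 2σ²(1 − r²)/m for ANCOVA. All three tests hold their size at about 5%. Power at 6:6 for 0.6 SD:

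| r | Follow-up only | Change t-test | ANCOVA |
|---|---|---|---|
| 0.3 | 15.7% | 12.5% | 15.5% |
| 0.5 | 15.6% | 15.5% | 17.5% |
| 0.7 | 15.6% | 22.9% | 23.7% |
| 0.8 | 15.6% | 31.8% | 31.5% |
| 0.9 | 15.6% | 55.5% | 52.7% |

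ANCOVA leads or nearly ties up to r = 0.8. Change scores are slightly better from 0.8 upward, because ANCOVA has 9 residual degrees of freedom instead of 10. The mean 95% CI half-width with ANCOVA is 1.16, 0.96 and 0.81 SD at r = 0.5, 0.7 and 0.8. An even split is not assured: if the 12 were a random draw from 32 + 32, exactly 6:6 would have probability 25%, and 4:8 or worse 34%.

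**Week 36.** Week 28 is day 196. The latest visit is 196 + 7 = day 203 and the latest PET/CT is 196 + 30 = day 226. Week 36 is day 252, which is 49 days after the first limit and 26 after the second.

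**Week 24 in Section 8.2.** The NIH Addendum places the second scan 24 weeks after study drug is completed. The last dose is at Week 4, so this is Week 28, as in Sections 1.3 and 8.1.

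**The case against.** The strongest defence is that no error in the t-test is proved. The objective speaks of the effect of CD24Fc, which points to a comparison of arms, and between arms an unpaired test is valid. TBR is exploratory, the scans are optional, the sentence sits in an assay section, and the SAP may settle the method. That much stands, and it keeps the point minor. It does not remove the ambiguity. The Section 3.1.6 endpoint speaks only of before and after therapy, whereas most Section 3.1.5 endpoints say between arms. A later SAP would also leave Section 8.2 contradicting it if another method were chosen.

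Several stronger readings are not supported.

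- A reader might infer that the unpaired test would produce false positives. With positively correlated scans it does the opposite: it is conservative.
- A reader might see a flat contradiction between Sections 8.2 and 9.4.2. Section 9.4.2 is headed primary and secondary, so a t-test for an exploratory subset could coexist with it. The tension arises because 9.4.2 names markers of vascular inflammation.
- A reader might infer that Appendix A moves the troponin endpoint to Week 36. Its own endpoint list keeps Week 28, so this is a slip in one clause of the analysis text.
- A reader might take week 24 as a scan four weeks early. The NIH Addendum largely explains it, and even study Week 24 (day 168) lies inside the PET window (days 166 to 226).

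**Conclusion.** The point holds as a minor one. Section 8.2 leaves the TBR comparison undefined. On the reading its wording suggests, the test is the wrong one for repeated scans and does not address drug against placebo. On the other reading it is valid but underspecified, and if only follow-up scans are compared it leaves the baseline scan unused. The size and power figures rest on assumed correlations, an assumed 0.6 SD effect, a 6:6 split and no dropout. What does not depend on them is that any positive correlation makes the before/after unpaired test conservative, and that such a test makes no comparison between arms. Every between-arm version has low power for a 0.6 SD effect over correlations of 0.3 to 0.8, so the PET data support estimation rather than a test.

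The Week 36 clause is wrong as written and needs no assumption to show it. The primary LDL analysis and its sample size are unaffected.

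**What to change.** In Section 8.2, replace the t-test sentence with text such as: *Week 28 TBR will be compared between arms by ANCOVA with baseline TBR as covariate, reporting the estimated difference and 95% CI. This analysis is exploratory and low-powered. Any within-arm change will be analysed as paired data and is descriptive.*

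With baseline as covariate, the treatment estimate is the same whether Week 28 TBR or change is the outcome. This is not true of percent change, which should be descriptive. A between-arm t-test on change is an acceptable alternative, and slightly more powerful if the correlation is 0.8 or higher; ANCOVA is preferred here because it follows Section 9.4.2. With 12 people, baseline TBR should be the only covariate.

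In the same text, give the repeat scan as Week 28 (24 weeks after the last dose). In the analysis text of Appendix A, change Week 36 to Week 28.

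The cost is wording only: both scans are already scheduled, and ANCOVA uses one degree of freedom.

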8.3 SAFETY AND OTHER ASSESSMENTS

Safety oversight will be conducted by collaboration between the Principal Investigator (PI), lead Study Coordinator (SC), the DSMB, and the Medical Monitor. A Medical Monitor (MM) has been appointed for

oversight of safety in this clinical study. If at any point in the trial halting rules are met, the study team (PI and SC) will arrange a (tele)conference so that the event can be reviewed and the discussion documented. At the end of each MM review meeting, the MM will be asked to provide a formal recommendation as to whether or not the protocol should be halted. A written summary of each MM review meeting will be provided to the MM and appropriate individuals. Participants on the MM teleconferences will include the MM, the PI and appropriate study team members. The MM will provide a written report to the DSMB as per Appendix A, Data Safety and Monitoring Plan (DSMP).

An independent DSMB has been established for oversight of safety in this clinical study, responsible to the NHLBI. This DSMB will be independent of regulatory agencies, IRB/EC, Oncolmmune, Inc, and investigators. See Appendix A for the Data Safety Monitoring Plan.

Subject safety will be monitored by the PI and study team. Clinical data and safety data will be monitored at least every 2 weeks (or less frequently, based on the SOA). An evaluation of safety and efficacy data will be obtained when the first 6 subjects complete 4 weeks of therapy by the appointed Medical Monitor. The Medical Monitor will not be part of the clinical staff caring for subjects during study visits, so blinding will be maintained. If concerns about the safety or efficacy arise, the Medical Monitor will refer concerns to the Sponsor and DSMB and review of adverse events will proceed per section 8 and the DSMP. Thereafter, safety and data analysis will be performed every 12 weeks through completion of the study. Additionally, the PI will be responsible for submitting the IRB Continuing Review package and will provide the necessary safety data for the FDA IND Annual Report.

All enrolled subjects who have received CD24Fc will be evaluated for safety with the laboratory assays done at each visit as outlined in section 8.2. Safety will be assessed by physical examination, vital signs, hematology, and chemistries. Vital signs will include pulse, blood pressure, respiratory rate, and oxygen saturation. The severity of signs, symptoms, and AEs will be determined by using DAIDS toxicity table, version 2.1, July 2017. The CD24Fc infusion will be administered over a minimum of 1 hour. Subjects will be monitored during and after infusion is completed for 2 hours every 30 minutes and repeat vital signs and laboratory results will be ascertained as needed based on reported symptoms.

In the event of abnormal laboratory tests, the tests will be repeated immediately if they are inconsistent with the subject's screening (baseline) laboratory results. If considered abnormal and deviating from baseline, they will be repeated and may be referred for physician sub-specialty consultation. These laboratory results will be repeated until they have returned to the normal range and/or an adequate explanation of the abnormality is found. If a clear explanation is established it should be recorded in the subject's study record.

8.4 ADVERSE EVENTS AND SERIOUS ADVERSE EVENTS

8.4.1 DEFINITION OF ADVERSE EVENTS (AE)

Adverse event means any untoward medical occurrence associated with the use of an intervention in humans, whether or not considered intervention-related.

8.4.2 DEFINITION OF SERIOUS ADVERSE EVENTS (SAE)

An adverse event (AE) or suspected adverse reaction is considered "serious" if, in the view of either the investigator or sponsor, it results in any of the following outcomes: death, a life-threatening adverse event, inpatient hospitalization or prolongation of existing hospitalization, a persistent or significant incapacity or substantial disruption of the ability to conduct normal life functions, or a congenital anomaly/birth defect. Important medical events that may not result in death, be life-threatening, or require hospitalization may be considered serious when, based upon appropriate medical judgment, they may jeopardize the participant and may require medical or surgical intervention to prevent one of the outcomes listed in this definition. Examples of such medical events include allergic bronchospasm requiring intensive treatment in an emergency room or at home, blood dyscrasias or convulsions that do not result in inpatient hospitalization, or the development of drug dependency or drug abuse.

8.4.3 CLASSIFICATION OF AN ADVERSE EVENT

8.4.3.1 SEVERITY OF EVENT

The investigator will grade the severity of each AE according to the "Division of AIDS Table For Grading The Severity Of Adult and Pediatric Adverse Events", version 2.1, July 2017. https://rsc.niaid.nih.gov/sites/default/files/daidsgradingcorrectedv21.pdf

For adverse events (AEs) not included in the protocol defined grading system, the following guidelines will be used to describe severity.

- **Grade 1-Mild** Causing no or minimal interference with usual social and functional activities with intervention not indicated.
- **Grade 2-Moderate** Causing greater than minimal interference with usual social and functional activities with intervention indicated.
- **Grade 3-Severe** Causing inability to perform usual social and functional activities with intervention or hospitalization indicated.
- **Grade 4-Potentially Life Threatening** Causing inability to perform basic self-care functions with intervention indicated to prevent permanent impairment, persistent disability or death.
- Grade 5-Death

8.4.3.2 RELATIONSHIP TO STUDY INTERVENTION

All adverse events (AEs) must have their relationship to study intervention assessed by the clinician who examines and evaluates the participant based on temporal relationship and his/her clinical judgment. The degree of certainty about causality will be graded using the categories below.

Definitely Related – There is clear evidence to suggest a causal relationship, and other possible contributing factors can be ruled out. The clinical event, including an abnormal laboratory test result, occurs in a plausible time relationship to study intervention administration and cannot be explained by concurrent disease or other drugs or chemicals. The response to withdrawal of the study intervention (dechallenge) should be clinically plausible. The event must be pharmacologically or phenomenologically definitive, with use of a satisfactory rechallenge procedure if necessary.

- **Probably Related** There is evidence to suggest a causal relationship, and the influence of other factors is unlikely. The clinical event, including an abnormal laboratory test result, occurs within a reasonable time after administration of the study intervention, is unlikely to be attributed to concurrent disease or other drugs or chemicals, and follows a clinically reasonable response on withdrawal (dechallenge). Rechallenge information is not required to fulfill this definition.
- **Potentially Related** There is some evidence to suggest a causal relationship (e.g., the event occurred within a reasonable time after administration of the trial medication). However, other factors may have contributed to the event (e.g., the participant's clinical condition, other concomitant events). Although an AE may rate only as "possibly related" soon after discovery, it can be flagged as requiring more information and later be upgraded to "probably related" or "definitely related", as appropriate.
- Unlikely to be related A clinical event, including an abnormal laboratory test result, whose temporal relationship to study intervention administration makes a causal relationship improbable (e.g., the event did not occur within a reasonable time after administration of the study intervention) and in which other drugs or chemicals or underlying disease provides plausible explanations (e.g., the participant's clinical condition, other concomitant treatments).
- Not Related The AE is completely independent of study intervention administration, and/or evidence exists that the event is definitely related to another etiology. There must be an alternative, definitive etiology documented by the clinician.

